The primary analysis population for upamostat is the modified intent-to-treat population, with a treatment arm consisting of all participants that were randomized to upamostat active treatment arm and received at least one dose of the active treatment. The control arm consists of all participants eligible to be randomized to upamostat that were randomized to placebo and received at least one dose of the placebo.

The primary analysis model is a Cox proportional hazards model for the time to alleviation or resolution of COVID-19 symptoms, with treatment arm (active upamostat vs placebo) as a covariate. The model estimated hazard ratio will be used as the estimator for the estimand of interest. The estimate and 95% confidence interval for the hazard ratio will be presented.

The primary hypothesis test is that upamostat increases the hazard (decreases time to resolution) of COVID-19 symptoms. A hypothesis test will be conducted for testing whether the upamostat hazard ratio is greater than 1 at a one-sided 2.5% level. One interim analysis will be conducted and a final analysis with type I error control over the two possible interims of 2.5%.

C 13.5 Outcome Measures and Statistical Analyses

C 13.5.1 Early Treatment

C 13.5.1.1 Primary Outcome

- Time to sustained alleviation or resolution of COVID-19 symptoms evaluated from Day 0 through Day 28 assessed via completion of a Daily Follow Up Symptom Questionnaire.

Sustained alleviation or resolution will be defined as the number of days from randomization to the first day the participant reports all symptoms as mild or none (≤ 1 or returning to pre-COVID-19 illness levels) for at least 3 consecutive days (the first day being considered the Event Day). Targeted symptoms will be used for analysis (Supplement 3 of the MP). Any patient that does not have alleviation or resolution of symptoms by Day 28 will be considered censored for alleviation or resolution at Day 28.

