The primary efficacy analyses will be conducted using the modified intention to treat (mITT) population. The primary analysis is a Cox proportional hazards model with treatment assignment as a fixed covariate with a proportional effect. A one-sided p-value for the test of a hazards ratio of 1 compared to the alternative of a hazard ratio greater than 1 (upamostat reduces time to resolution of symptoms) will be presented and used for testing superiority. An interim analysis will be conducted when 50% of maximum enrollment has reached 28 days of exposure. A Kim-Demets (with parameter 2) spending function will be utilized for testing for superiority of upamostat at the interim and final analysis. At the interim analysis, futility analyses will be conducted, where enrollment to the upamostat cohort will be stopped if the predictive probability of superiority by the final sample size is less than 5%.

The hazard ratio for the time to resolution of COVID-19 will be presented with 95% confidence intervals. Additional sensitivity analyses for the primary analysis will utilize additional covariate adjustments in the Cox proportional hazards model.

C 13.5.1.2 Secondary Outcome: Clinical

For each analysis, a 5% two-sided significance will be used. 95% confidence intervals will be presented to summarize each effect estimate. Dichotomous outcomes will be summarized with relative proportions. Ordinal outcomes will be summarized with stacked bar plots, cumulative proportion graphs, and percentiles. Kaplan-Meier plots will be used for summarizing time to event outcomes. Continuous measures will be summarized box plots (means, medians, and inter-quartile ranges).

Each of the secondary analyses will be conducted using the modified intention to treat (mITT) population. Each analysis will be repeated using the per protocol population.

- Change in overall COVID-19 symptom severity score from Day 0 through Day 28

The overall symptom severity question on the Daily Symptom Follow Up Questionnaire will be used for this secondary endpoint. A mixed model repeated measure (MMRM) model will be

used to model the symptom severity score at each day using the baseline symptom score, participant, day, and treatment by day as covariates. The treatment effect by day will be summarized.

- Proportion of participants in each treatment group developing new COVID-19 symptoms rated as severe from Day 0 to Day 28

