- Comparison between active and placebo treatment groups in proportion of all and \geq grade 3 adverse events as assessed by the National Institutes of Health, Division of AIDS Table for Grading the Severity of Adult and Pediatric Adverse Events (DAIDS AE Grading Table), corrected Version 2.1, July 2017.
- Incidence of AEs causing IP discontinuation
- Incidence of all-cause IP discontinuation or interruption
- Number of participants hospitalized due to adverse events regardless of cause

All adverse events will be listed by participant and will include:

- Event description
- Treatment group (active agent vs placebo)
- Clinician's assessment of severity and relationship to upamostat
- Outcome

The number and percentage of participants with AEs will be summarized for each treatment group. Overall treatment group differences may be compared using Chi-square tests or Fisher's exact tests.

Serious AEs, TEAEs, and hypersensitivity reactions will also be summarized. The counts and proportion of participants experiencing these events will be reported for each treatment arm. Treatment groups may be compared by Chi-square tests or Fisher's exact tests.

Permanent discontinuations or interruptions of upamostat due to AEs will be listed. The count and proportion of discontinuations of the study drug due to AEs will be reported.

Categorical safety measures including hospitalization will be summarized with counts and proportions of participants and may be compared by treatment using either a Chi-square test or a Fisher's exact test.

C 13.5.1.4 Exploratory

Prevalence and titer of anti-SARS-CoV-2 IgM and IgG antibodies at baseline and at Week 8 will be determined, and the effect of presence and titer of anti-SARS-CoV-2 IgG at baseline on treatment outcome will be assessed.

For participants receiving upamostat, targeted analysis of known host transmembrane protease polymorphisms will be described and compared to time to resolution of symptoms among key subgroups including by sex, race, and ethnicity.

C 13.5.1.5 Sub-Group Analyses

The primary analysis and each of the secondary analyses will be conducted in different patient subgroups of the mITT population for exploration of heterogeneity of treatment effect. The following patient subgroups will be analyzed:

- Age (< 30, 30-50, >50 years old)
- Sex
- Race
- Baseline symptom severity
- SARS-CoV-2 vaccination status
- Location (by continent)

C 13.6 Interim Analysis Plan

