5.2. Efficacy Assessments

The key efficacy assessment in the early treatment indication is time to sustained alleviation or resolution of symptoms among patients who were SARS-CoV-2 positive on initial screening at a local laboratory, either by PCR or rapid antigen test. Time to sustained alleviation or resolution of targeted COVID-19 symptoms will be defined as the number of days from randomization in a PSA (Step 2 of randomization) to the first day the participant reports all symptoms as mild or none (≤ 1 on the Daily Follow Up Symptom Questionnaire), or no worse than the usual severity, for at least 3 consecutive days (the first day being considered the Event Day).

Targeted symptoms include stuffy or runny nose, hoarse voice, sore throat, difficulty breathing, cough, fatigue, muscle or body aches, headache, chills or shivering, feeling hot or feverish, nausea, vomiting, diarrhea, loss of taste, loss of smell. The Symptom Severity Score is collected in the Symptom Follow Up Questionnaire as the Overall Symptom Severity. Overall Symptom Severity may be rated none (0), mild (1), moderate (2), or severe (3). Loss of taste and loss of smell may be rated as the same as usual (0), less than usual (1), or no sense of taste/smell (2, considered a “severe” rating).

The general statistical approach will compare outcomes among participants randomized to receive the active agent, upamostat, to outcomes among participants who were eligible to have been randomized to upamostat but who were randomized instead to any of the placebo arms enrolling at that time. This ensures that the comparison is limited to concurrently randomized participants eligible to receive upamostat.

Unless otherwise specified, for each analysis, a 5% two-sided significance will be used. 95% confidence intervals will be presented to summarize each effect estimate. Dichotomous outcomes will be summarized with relative proportions. Ordinal outcomes will be summarized with stacked bar plots, cumulative proportion graphs, and percentiles. Kaplan-Meier plots will be used for summarizing time to event outcomes. Continuous measures will be summarized with box plots (means, medians, and inter-quartile ranges).

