Sustained alleviation or resolution will be defined as the number of days from randomization within a PSA to the first day the participant reports all symptoms as mild or none (≤ 1 or returning to pre-illness levels) for at least 3 consecutive days (the first day being considered the Event Day). Targeted symptoms will be used for analysis (Supplement 3). Symptoms will be collected at Enrollment using the Screening Symptom Questionnaire to establish baseline symptom status.

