5.2.1. Primary Outcome

- Time to sustained alleviation or resolution of COVID-19 symptoms evaluated from Day 0 through Day 28 assessed via completion of a Daily Follow Up Symptom Questionnaire
 - Analysis population: mITT

The primary objective is to estimate the relative time to sustained alleviation or resolution of symptomatic COVID-19 infection for a participant that receives upamostat compared to a participant that does not receive upamostat.

The primary analysis population is the Modified Intent-to-Treat Population.

The estimand of interest is the hazard ratio of a participant that has symptomatic COVID-19 with standard of care background therapy when starting treatment with upamostat compared to no upamostat. A hazard ratio greater than 1 indicates a shorter time to resolution of symptomatic COVID-19 infection

The primary analysis model is a Cox proportional hazards model for the time to alleviation or resolution of COVID-19 symptoms, with treatment arm (active upamostat vs placebo) as a fixed

covariate with proportional effect. The model estimated hazard ratio will be used as the estimator for the estimand of interest. The estimate and 95% confidence interval for the hazard ratio will be presented.

The primary hypothesis test is that upamostat increases the hazard (decreases time to resolution) of COVID-19 symptoms. A hypothesis test will be conducted for testing whether the upamostat hazard ratio is greater than 1 at a one-sided 2.5% level.

Additional sensitivity analyses for the primary analysis will utilize additional covariate adjustments in the Cox proportional hazards model. The analysis will be repeated for the Per Protocol Population and the Baseline COVID-19 PCR Positive Population.

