5.2.2. Secondary Outcomes: Clinical

- Number and proportion of all cause hospitalizations
 - Timeframe: Day 0 to Day 28
- Number and proportion of all cause deaths
 - Timeframe: Day 0 to Day 28
- Change in overall COVID-19 symptom severity score
 - Timeframe: Day 0 to Day 28
 - A mixed model repeated measure model will be used to model the symptom severity score (Overall Symptom Severity) at each day using the baseline symptom score, participant, day, and treatment by day as covariates. The treatment effect by day will be summarized.
- Number and proportion of participants in each treatment group developing new COVID-19 symptoms rated as severe
 - Timeframe: Day 0 to Day 28
 - A Cox proportional hazards model will be used to analyze development of new severe symptoms. A new severe symptom is defined as scoring from 0 to 1 on any symptom in the questionnaire and subsequently scoring a 3 for that symptom (or a 2 for change in taste or smell). Treatment arm will be modeled with a proportional hazard effect. The hazard ration will be summarized.
- Proportion of participants who report a return to usual state of health
 - Timeframe: Day 7, Day 14, Day 28, Week 8, Week 12
 - A Cox proportional hazards model will be used to analyze the rime to return to usual state of health. Participants without symptomatic COVID-19 will be considered a 0 for return to usual health. Treatment arm will be modeled with a proportional hazard effect. The hazard ration will be summarized.
 - A Kaplan-Meier curve of time to return to usual state of health will be presented.
- Proportion of participants who report a return to usual activities
 - Timeframe: Day 7, Day 14, Day 28, Week 8, Week 12
 - A Cox proportional hazards model will be used to analyze the time to return to usual activities. Participants without symptomatic COVID-19 will be considered a 0 for return to usual activities. Treatment arm will be modeled with a proportional hazard effect. The hazard ratio will be summarized.
 - A Kaplan-Meier curve of time to return to usual activities will be presented.

Analysis population: The mITT population will be used for secondary endpoint analyses. Change in overall COVID-19 symptom severity score will be repeated with the Per Protocol Population and the Baseline COVID-19 PCR Positive Population.

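### The primary Cox model has treatment as its only term; adding baseline symptom severity would gain a few points of power if severity is prognostic, and nothing if it is not

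*SAP*

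**What the plan says.** The primary analysis has one explanatory term in both documents. SAP 5.2.1 fits a Cox model "with treatment arm (active upamostat vs placebo) as a fixed" covariate. Protocol C 13.4 describes it "with treatment arm (active upamostat vs placebo) as a covariate", and C 13.5.1.1 repeats: "The primary analysis is a Cox proportional hazards model with treatment assignment as a fixed covariate with a proportional effect".

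Baseline severity appears elsewhere in the plan:

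- SAP 5.2: "Symptoms will be collected at Enrollment using the Screening Symptom Questionnaire to establish baseline symptom status".
- SAP 5.2.2: the mixed model for overall symptom severity is fitted "at each day using the baseline symptom score, participant, day, and treatment by day as covariates".
- Protocol C 13.5.1.5 lists "Baseline symptom severity" among the subgroup factors for the primary and secondary analyses. The SAP 5.2.5 list does not carry it over.

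Adjustment of the primary endpoint is planned only as a sensitivity analysis, with no covariate named: "Additional sensitivity analyses for the primary analysis will utilize additional covariate adjustments in the Cox proportional hazards model".

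**The concern.** The event requires every targeted symptom to fall to mild or none, or to its usual level, for three consecutive days. A participant who starts with worse symptoms has further to go, so baseline severity is a plausible predictor of time to event. A Cox model that omits a prognostic covariate gives a valid but less powerful test.

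Achieved size makes this more relevant. SAP Appendix A records that enrollment ended before the interim trigger, which protocol C 13.6 sets at 150 participants reaching Day 28. The final N is not stated. If it fell well short of 300, power fell with it, and adjustment is one of the few ways to recover some without new participants. Leaving the sensitivity covariates unnamed also means that the adjusted model is not fixed in advance.

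**Working it through.** **1. Reproduce the stated power.** Inputs from protocol C 13.4, C 13.5.1.1, C 13.6 and C 13.9: 150 per arm, control median 9 days, censoring at Day 28, hazard ratio 1.50, one-sided 2.5%. Exponential times are assumed.

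- Control still unresolved at Day 28: exp(−ln 2 × 28/9) = 0.116. Active: exp(−1.5 × ln 2 × 28/9) = 0.039.
- Expected events: 150 × (0.884 + 0.961) = 276.7.
- Expected z = ln(1.50) × √(276.7/4) = 3.37. Single-test power = Φ(3.37 − 1.96) = 92.1%.
- With the protocol's two looks (nominal alphas 0.00625 and 0.02178), power is 91.5% against 0.906 in Table 3. At hazard ratio 1.42 it is 81.9% against 0.812.

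The plan's figure reproduces. Table 3 rests on log-rank simulations with no covariate described, so 1.50 is read as an unadjusted hazard ratio.

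**2. Half the planned size.** At an illustrative N=150 there are 138.3 expected events, z = 0.4055 × √(138.3/4) = 2.38, and power is about 66%.

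**3. Add baseline severity.** The documents give neither the prognostic strength nor the severity distribution, so both are assumptions. Strength is expressed as the SD of the log hazard due to severity. Each cell has 10,000 simulated trials with 1:1 allocation and times rounded up to whole days. The conditional hazard ratio is calibrated so that the unadjusted one stays at 1.50. There is a single final test at z > 1.96, as in the SAP. Both models are fitted to the same data. The Monte Carlo SE of the gain is at most 0.33 points for SD up to 0.3.

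| Covariate entered | SD | N=300, unadjusted → adjusted | N=150, unadjusted → adjusted |
|---|---|---|---|
| Three levels (27/51/22%) cut from continuous severity | 0 | 92.2 → 92.0% | 66.5 → 66.5% |
| | 0.2 | 92.3 → 93.3% (+1.0) | 65.6 → 67.8% (+2.2) |
| | 0.3 | 91.5 → 93.5% (+2.0) | 65.6 → 70.0% (+4.4) |
| Two levels (50/50) | 0.2 | +1.0 | +1.5 |
| | 0.3 | +2.3 | +3.3 |
| Three-level score carrying the whole SD | 0.2 | +1.4 | +2.5 |
| | 0.3 | +3.0 | +5.4 |

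The squared ratio of mean z values puts the gain at about 4–6% more participants at SD 0.2 and 8–13% at SD 0.3. A three-level covariate at SD 0.5 gives +5.1 and +10.4 points.

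**4. What these SDs mean.** A 0/1/2 score with 27/51/22% has mean 0.95, variance 1.39 − 0.9025 = 0.4875 and SD 0.70. If it carries the whole SD of 0.2, the severe-versus-mild hazard ratio for resolution is exp(−2 × 0.2/0.70) = 0.56. For SD 0.3 it is 0.42.

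**5. Cross-check with another parametrization.** Severity at 30/50/20% (score SD 0.70), resolution hazard multiplied by a fixed factor per step, unadjusted hazard ratio held at about 1.50:

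| Factor per step | Implied SD = \|ln factor\| × 0.70 | Gain, N=300 | Gain, N=150 |
|---|---|---|---|
| 0.8 | 0.16 | +0.9 | +1.9 |
| 0.7 | 0.25 | +2.2 | +3.8 |
| 0.6 | 0.36 | +4.2 | +8.2 |

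At N=300 these fall in line with the first table; at N=150 they agree broadly.

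**6. Side effects.** Type I error is 2.1–2.6% with and without adjustment. The adjusted hazard ratio averages about 1.52 at SD 0.2 and 1.54 at SD 0.3, because a conditional hazard ratio differs from a marginal one.

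**The case against.** A treatment-only primary model with adjusted sensitivity analyses is a legitimate choice. It matches the protocol and the log-rank basis of the sample size, so nothing is broken. That stands: the point is about efficiency.

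The mixed model is weak precedent, since adjusting a change in severity for its own baseline is natural and does not oblige the Cox model to follow. That is fair. It shows only that the plan expects a baseline score to be available.

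Availability itself is not settled. The 0–3 overall severity item is described for the Follow Up Questionnaire, whereas baseline status comes from the Screening Symptom Questionnaire, whose coding is not in the supplied text. The SAP also dropped the protocol's severity subgroup without giving a reason. Both must be resolved before the covariate is named.

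The gain needs fairly strong prognosis. A severe-versus-mild hazard ratio of 0.56 to 0.42 is a larger effect than the drug's assumed 1.50 (inverse 0.67). At SD 0.1, where severe versus mild is about 0.75, smaller simulations put the gain at 0.3 to 0.7 points at N=300 and 0.9 to 1.8 at N=150. This limits the size but leaves the direction unchanged.

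Finally, the SAP was signed on 28 July 2025, after enrollment ended, and changing the primary model now departs from the protocol. That is a real cost, and it is why a fallback is needed.

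**Conclusion.** The point holds as an improvement worth making, with medium confidence. It does not challenge the validity of the test or the stated power. For a log-hazard SD of 0.2 to 0.3, adjustment adds about 1 to 3 points of power at N=300 and 2 to 5 at N=150. For very weak prognosis the gain at N=300 is under 1 point, and with no prognosis it is nil.

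The size depends on assumed prognostic strength, an assumed severity distribution and an unadjusted hazard ratio of 1.50. If the conditional hazard ratio were 1.50 instead, the gain would be larger (about 6 points at N=300 for a factor of 0.6 per step), because unadjusted power would itself drop to about 85%. N=150 is only an illustration. The SAP also expands Master Protocol Section 13, and randomization details sit in a separate form. Neither was supplied, so covariates or stratification factors named there cannot be excluded.

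**What to change.** 1. Check the Master Protocol and the Request for Randomization form for covariates or stratification factors already named.
2. If the data are still blinded, add to the primary Cox model the baseline symptom score used in the SAP 5.2.2 model, or another usable severity item from the enrollment questionnaire. Log it in SAP Appendix A as a change from the protocol made before unblinding.
3. State the item, its coding (for example one linear term) and a rule for a missing baseline value, so that no mITT participant is lost. SAP 4.10 imputes nothing unless specified.
4. State that the primary hazard ratio is then conditional on baseline severity, and report the treatment-only model as supportive.
5. If unblinding has occurred or the primary model cannot change, keep it, name this covariate in the adjusted sensitivity model, and state when it was chosen.

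The cost is one or two degrees of freedom, and no new data if the baseline item is usable. The primary hazard ratio changes meaning slightly, and the primary model departs from the protocol late in the trial. The fallback needs only a SAP addendum.

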5.2.2. Secondary Outcomes: Clinical

- Number and proportion of all cause hospitalizations
 - Timeframe: Day 0 to Day 28
- Number and proportion of all cause deaths
 - Timeframe: Day 0 to Day 28
- Change in overall COVID-19 symptom severity score
 - Timeframe: Day 0 to Day 28
 - A mixed model repeated measure model will be used to model the symptom severity score (Overall Symptom Severity) at each day using the baseline symptom score, participant, day, and treatment by day as covariates. The treatment effect by day will be summarized.
- Number and proportion of participants in each treatment group developing new COVID-19 symptoms rated as severe
 - Timeframe: Day 0 to Day 28
 - A Cox proportional hazards model will be used to analyze development of new severe symptoms. A new severe symptom is defined as scoring from 0 to 1 on any symptom in the questionnaire and subsequently scoring a 3 for that symptom (or a 2 for change in taste or smell). Treatment arm will be modeled with a proportional hazard effect. The hazard ration will be summarized.
- Proportion of participants who report a return to usual state of health
 - Timeframe: Day 7, Day 14, Day 28, Week 8, Week 12
 - A Cox proportional hazards model will be used to analyze the rime to return to usual state of health. Participants without symptomatic COVID-19 will be considered a 0 for return to usual health. Treatment arm will be modeled with a proportional hazard effect. The hazard ration will be summarized.
 - A Kaplan-Meier curve of time to return to usual state of health will be presented.
- Proportion of participants who report a return to usual activities
 - Timeframe: Day 7, Day 14, Day 28, Week 8, Week 12
 - A Cox proportional hazards model will be used to analyze the time to return to usual activities. Participants without symptomatic COVID-19 will be considered a 0 for return to usual activities. Treatment arm will be modeled with a proportional hazard effect. The hazard ratio will be summarized.
 - A Kaplan-Meier curve of time to return to usual activities will be presented.

Analysis population: The mITT population will be used for secondary endpoint analyses. Change in overall COVID-19 symptom severity score will be repeated with the Per Protocol Population and the Baseline COVID-19 PCR Positive Population.

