- Screening Symptom Questionnaire (repeat if visit not performed on same day as Screening)
- Randomization (Step 1)
- Study (IP) Informed Consent (in person)
- Screening assessments (see [Section C 9.2.3 Screening Assessments](#))
- **ECG**
- Eligibility evaluation (review of all screening and eligibility assessments)
- Randomization (Step 2)
- Upper respiratory specimen collection (prior to administration of upamostat or control) (for efficacy assessment)
- Venous blood sampling (prior to administration of upamostat or control)
 - Hematology (prior to administration of upamostat or control)
 - Chemistry (prior to administration of upamostat or control)
 - **Coagulation Studies**
 - **Anti-SARS-CoV-2 IgM and IgG**
 - **Polymorphisms of relevant host cellular proteases**
 - **Whole Blood, Plasma and Serum Storage for Possible Future Research (prior to administration of upamostat or control)**
 - **Pharmacokinetics**
- **Administration of upamostat or control**
- Collect and update contacts
- Dispense study kit
- Adverse event recording and reporting

C9.4.3 Day 3 Visit – ~~Remote~~ or In Person

This visit is scheduled to take place In Person on Day 3. Every effort should be made to complete the Day 3 visit requirements on Day 3; however, the visit may take place — if necessary +/- 1 days.

- ~~SARS-CoV-2 Vaccination Status~~
- Concomitant medication review
- Collect and update contacts
- Daily Symptom Follow Up Questionnaire (daily until day 28 then at **Weeks 8** and 12)
- Upper respiratory specimen collection
- Clinical outcome assessment
- Vital signs
- Physical exam
- Venous blood sampling (for Pharmacokinetics Group A: venous blood sampling should be collected within 2 hours prior to administration of upamostat or control, for Pharmacokinetics Group B: venous blood sampling should be collected 2-4 hours after administration of upamostat or control)
 - Hematology
 - Chemistry
 - **Coagulation studies**
 - **Whole blood, plasma, and serum storage for possible future research**
 - **Pharmacokinetics**
- **ECG**
- Adverse event recording and reporting

C 9.4.4 Day 7 Visit- ~~Remote~~ or In-person

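### Overall symptom severity is reported only as a treatment effect on each of about 28 days; no single contrast is named as the endpoint's answer.

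*SAP*

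**What the plan says.** SAP 5.2.2 states: "A mixed model repeated measure model will be used to model the symptom severity score (Overall Symptom Severity) at each day". The model terms, and the only output described, follow: "using the baseline symptom score, participant, day, and treatment by day as covariates. The treatment effect by day will be summarized". The window is "Timeframe: Day 0 to Day 28". Protocol C 13.5.1.2 specifies the same model and output.

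The score is the single 0-to-3 overall item of the symptom questionnaire (SAP 5.2). The protocol's visit sections collect it each day: "Daily Symptom Follow Up Questionnaire (daily until day 28 then at" Weeks 8 and 12.

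On error level, protocol C 13.5.1.2 says of the secondary outcomes: "For each analysis, a 5% two-sided significance will be used". SAP 5.2 says: "Unless otherwise specified, for each analysis, a 5% two-sided significance will be used". Both add a 95% interval for every effect estimate. Nothing in the text for this endpoint sets a different rule.

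SAP 5.2.2 repeats the endpoint in the Per Protocol and baseline PCR-positive populations, and SAP 5.2.5 extends the secondary analyses to subgroups.

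**The concern.** A repeated-measures model can answer several questions: the difference on one day, the average difference over the follow-up, or whether the two profiles differ at all. The plan asks for all the daily differences and does not say which result, or which combination, answers the objective that upamostat reduces disease severity. A statistician who follows the text exactly finishes with about 28 estimates, 28 intervals and no rule for reading them together.

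Two things are at stake. First, once results are known, a favourable day could be put forward as the finding, and nothing in the plan would mark that as selective. Second, a single day uses the diary data poorly if the effect is spread over many days.

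The model is also loosely worded. It lists participant among the covariates without saying that participant is the unit of repetition, and it names no covariance structure. Two programmers could fit different models from the same text.

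**Working it through.** **No figure to reproduce.** The documents give no sample size, power or error rate for this endpoint.

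**Inputs from the documents.** Daily scores to Day 28, with Day 0 taken as the baseline covariate, give 28 post-baseline days. The level is 5% two-sided for each effect, unadjusted.

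**Assumed input.** The documents give no correlation between daily treatment estimates, so I show a range. It is the between-day correlation of a participant's scores after baseline adjustment. With complete data, sample size does not enter the null calculation.

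**Independent days (upper bound of the range shown).** Chance of at least one day with p<0.05 under no effect: 1 − 0.95^28 = 0.762. With 29 days it is 1 − 0.95^29 = 0.774. For days favouring upamostat only: 1 − 0.975^28 = 0.508.

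**Correlated days.** I simulated 28 null z-statistics (400,000 draws per setting) and counted draws with any |z| > 1.96, and draws with any z > 1.96 in upamostat's favour.

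| Correlation between days | Either direction | Favouring upamostat |
|---|---|---|
| AR(1) 0.50 | 0.71 | 0.44 |
| AR(1) 0.70 | 0.62 | 0.35 |
| AR(1) 0.80 | 0.53 | 0.29 |
| AR(1) 0.90 | 0.39 | 0.20 |
| AR(1) 0.95 | 0.27 | 0.14 |
| AR(1) 0.98 | 0.17 | 0.09 |
| Equal correlation 0.30 | 0.64 | 0.34 |
| Equal correlation 0.50 | 0.49 | 0.25 |
| Equal correlation 0.70 | 0.33 | 0.17 |
| Equal correlation 0.90 | 0.17 | 0.08 |

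A random intercept plus AR(1) gives 0.25 to 0.43 in either direction. The either-direction chance passes 50% only if the AR(1) correlation is below about 0.83 or the equal correlation is below about 0.49. Across the range the chance is 0.17/0.05 ≈ 3 to 0.76/0.05 ≈ 15 times the nominal level.

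**With one named contrast.** The error rate for the endpoint is 0.05 two-sided. Keeping all 28 days as tests under Bonferroni would need 0.05/28 = 0.0018 per day.

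**Precision, for illustration only.** Assume 75 per arm and a constant shift of 0.3 SD on every day; neither comes from the documents. For one day, z = 0.3 × √(75/2) = 1.84, so power is Φ(1.84 − 1.96) ≈ 45%. For the 28-day average, divide z by the square root of the mean entry of the AR(1) correlation matrix:

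- Correlation 0.80: mean entry 0.271, z = 3.53, power 94%.
- Correlation 0.90: mean entry 0.461, z = 2.71, power 77%.
- Correlation 0.95: mean entry 0.654, z = 2.27, power 62%.

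**Covariance.** An unstructured matrix over 28 days has 28 × 29/2 = 406 parameters.

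**The case against.** The best defence is that the plan says the daily effects are summarised, not tested. The mixed model can be read as one analysis, and neither document says that each day is tested or that any one day counts as success. That stands as a reading of the words: a reader might infer that 28 hypothesis tests are written into the plan, and they are not. It does not remove the problem. The default level and the 95% interval attach to each effect estimate, a 95% interval on a day can be read as a 5% test of that day, and no other result is named for the endpoint.

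Other stronger readings are also unsupported:

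- **A chance significant day is likely.** The scores are a 0-to-3 item from the same people on successive days. If they are strongly correlated, the chance is below one half, and counting only favourable days it falls further. The documents do not settle the correlation.
- **The listed model cannot be estimated.** If participant were a fixed effect, it would absorb baseline score and arm, and only 27 of 28 daily effects would be estimable. A mixed model for repeated measures does not imply that, so this is a matter of wording.
- **A treatment main effect is missing.** Day plus full treatment-by-day spans the same space with or without it (rank 56 either way). Any average can be computed from the listed model.
- **The power comparison shows a known loss.** It rests on assumed inputs. A constant shift over 28 days also sits uneasily with the protocol's expected 9-day control median, since later differences would probably shrink.

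It is also fair that this is one of four endpoints under the disease-severity objective of a phase 2 trial.

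**Conclusion.** The concern holds in a limited form. The endpoint has about 28 answers and no rule for choosing among them. With no treatment effect, the chance of at least one nominally significant day is about 17% to 76%, according to the assumed between-day correlation. The corresponding chance for a day favouring upamostat is about 8% to 51%. The missing contrast is plain from the text and does not depend on where in that range the truth lies.

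A reader might infer that the trial's main conclusion is exposed. It is not: the primary Cox analysis has its own one-sided 2.5% test (SAP 5.2.1) and does not draw on this model. This is a change that should be made, not one on which the trial's validity turns.

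**What to change.** In SAP 5.2.2, before unblinding:

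1. Name one contrast from the planned model as the endpoint's estimate. One sound choice is the least-squares mean treatment difference averaged with equal weight over Days 1 to 28, tested once at 5% two-sided with its 95% interval. An area under the curve, a single named day or a joint test would also be defensible; the need is to choose one.
2. Label the daily effects descriptive and show them without p-values.
3. State that participant is the repeated-measures unit, and name a feasible structured covariance instead of leaving open an unstructured 28 × 28 matrix. Robust standard errors would guard against a wrong choice.
4. Say which day numbering the average uses. The protocol calls enrollment Day 0, whereas the Study Day formula in SAP 4.10 makes the day of first dose Day 1.

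The cost is wording: the data and model family stay the same. There are two downsides. An average over 28 days can dilute an effect confined to the early days, which is a reason to settle the contrast on clinical grounds now. SAP version 1.0 has also been signed, so the change and its timing relative to unblinding must be recorded as SAP section 1 and Appendix A require. The documents reviewed do not show whether unblinding has taken place. If it has, the contrast should be reported as chosen afterwards.
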